Decrements in **cognitive performance** occur when core temperature increases by about 1°C (Reinersten et al., 2008; Simmons et al., 2008). The level of cognitive decline depends on exposure duration, the intensity and complexity of the activity, and— importantly— the degree of hyperthermia (Gaoua et al., 2011; Simmons et al., 2008). There have been several heat stress studies performed in industrial settings and in climatic heat chambers. Processing speed and reaction time, short-term memory, and decision are all impaired (Gaoua et al., 2011; Sun et al., 2012; Piil et al., 2017; Mazlomi et al., 2017).

Cooling the skin reduces the unpleasant sensations caused by excessive heat exposure (Simmons et al., 2008). Localized cooling of the torso during systemic heat exposure reduces physiological stress by lowering body skin and core temperatures, decreasing heart rate, reducing sweat rate, and improving perception of thermal comfort (Chang, Song, & Yang, 2015). **Cooling vests** worn under impervious surgical gowns serve as a heat sink and reduce unpleasant sensations and the symptoms of physiological stress (Smolander et al., 2004; Kenney et al., 2011; Reinersten et al., 2008).

We propose to test the primary hypothesis that **wearing a cooling vest during surgery improves surgeons' perception of thermal comfort**. Secondary, we will test the hypothesis that **wearing a cooling vest during surgery reduces surgeons' mean-body temperature and preserves their cognitive performance**.

Specific Aims

1. Our **primary aim** is to evaluate surgeons' self-rated thermal comfort with and without a cooling vest during prolonged and strenuous surgery.
Primary hypothesis: Surgeons' self-rated thermal comfort is improved by wearing a cooling vest during prolonged and strenuous surgery.
2. A **secondary aim** is to evaluate surgeons' mean-body temperature with and without a cooling vest during prolonged and strenuous surgery.

Secondary hypothesis 1: Surgeons' mean-body temperature, estimated from core and mean-skin temperature, is reduced by wearing a cooling vest during prolonged and strenuous surgery.

3. Another **secondary aim** is to evaluate surgeons' cognitive performance with and without a cooling vest just after prolonged and strenuous surgery.

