Surgeons will be randomly assigned to use either the CoolSource™ cooling vest (worn between scrubs) and a conventional surgical gown for each of 4 surgeries. Sequence of treatments within surgeons will be randomized (ABBA, BAAB, AABB or BBAA), and determined using the PLAN procedure in SAS, such that each surgeon will wear vest and non-vest twice. The sequencing will not be shared with any study personnel. Allocation for each case will be concealed with a web-based system that will be accessed only shortly before surgery.

We will target an ambient temperature of $21^{\circ}\text{C} \pm 1^{\circ}\text{C}$, and try to maintain the same temperature of each of the four study cases for each surgeon. The CoolSource vest holds six reusable cooling packs

located bilaterally on the shoulders, angled flank along the base of the rib cage, and along each side of the spine, mid-back. The vest will be donned over hospital-issued scrubs after all temperature sensing devices have been applied and before surgical hand scrubbing. Surgeons will wear the vest throughout surgery, and for a few additional minutes while postoperative assessments are made (details below).

The weight of the disposable cooling vest is 1 kg which is evenly distributed over both shoulders. The cooling packs have an insulated cover to reduce condensation or sweating while seated inside the vest pocket. The flexible frozen reusable cooling packs will be inserted into each of the six pockets and the vest belt will be tied to hold the cooling packs securely. The disposable cooling vests will be discarded after each case, and the cooling packs returned to a freezer.

Measurements

A questionnaire detailing demographic information (age, height, weight, age, ethnicity, and education level) training level, specialty program, and estimated past case volume will be completed by participating surgeons before their first case.

Temperature of the freezer holding the cooling packs will be assessed before randomization to confirm that the temperature is <0°C.

Before every surgical case starts the time the surgeon dons the cooling vest and the time the surgeon dons the sterile surgical gown will be recorded.

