Primary Outcome will be self-rated thermal comfort. Immediately after surgery, *while still gowned*, surgeons will rate their thermal comfort on a 0-10 Likert scale, with 0 representing extreme cold, 5 being thermal comfort, and 10 representing extreme heat. Two points on the 11-point Likert scale will be considered a clinically important difference.

Secondary Outcome #1 - mean core temperature. The first secondary outcome will be the mean core temperature for a case, calculated as the time-weighted average over the taken measurements. The surgeon's core body temperature will be monitored by a validated wireless wearable iThermonitor WT701 biosensor which estimates core temperature within $\pm 0.5^{\circ}\text{C}$ (Pei et al., 2018). The sensor will be applied to the surgeon's right axilla 15-20 minutes prior to the surgical hand scrub performed at the start of surgery and secured with an adhesive cover. A small patch of axillary hair will be clipped or shaved as necessary. After the temperature sensors are applied, the surgeon's oral temperature will be measured by the Femometer adult digital oral thermometer which meets professional accuracy standards for digital thermometers (ASTM E1112-00) to support the accuracy of the iThermonitor core body temperature measurement. The surgeon's oral temperature will be measured for a second time when the surgeon exits the surgical field prior to taking the C3B battery assessment.

Secondary Outcome #2 - mean skin temperature. The second secondary outcome will be the mean skin temperature for a case, calculated as the time-weighted average over the taken measurements. Mean skin temperature will be estimated from skin temperature from the back of the upper chest, deltoid arm, thigh, and calf using the formula $[\text{MST}_R = 0.3 t_{\text{chest}} + 0.3 t_{\text{arm}} + 0.2 t_{\text{thigh}} + 0.2 t_{\text{leg}}$ or $0.3(t_{\text{chest}} + t_{\text{arm}}) + 0.2(t_{\text{thigh}} + 0.2 t_{\text{leg}})]$ (Ramanathan, 1964). Skin temperature will be continuously measured using wireless patches, TempTraq, which meet professional accuracy standards for digital thermometers (ASTM E1112-00). The sensors will remain affixed with adhesive dressing on the surgeon's body surface throughout surgery and approximately 10 minutes required for post-operative testing.

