Secondary Outcome #3 will be surgeons' cognitive performance, measured with the C3B battery. The self-administered C3B is a performance-based battery of cognitive tests which measure visual memory; episodic learning and delayed memory (five learning trials with a total score of 70) and processing speed; information processing speed and incidental memory (15 symbols repeated for 120 seconds). Also, relevant distractions or interruptions (phone call, pager, staff, equipment, and other) will be recorded and the frequency in which they occur during the C3B battery test. Both tests will be aggregated using z-scores and summing the z-scores within patient. A greater than 10% within-subject difference in total scores will be considered significant. Testing will take place right after surgery with surgeons still gowned. The surgeons will sit with the iPad touch screen placed on a desk in front of them for approximately 10 minutes to complete the cognitive test. To minimize learning during the trial, participating surgeons will complete the cognitive assessment battery before the first study day. For subsequent cases, the test will be administered prior to the surgical hand scrub and after the end of surgery. The C3B test modules use auditory test instructions and on-screen visual test stimuli consistent with symbols, single digits, and single letters.

Secondary Outcome #4 will be surgeon' perceived ergonomic workload measured with Borg CR₁₀ scale of exertion and the rating-of-fatigue (ROF) scale.

Immediately after surgery, *while still gowned*, surgeons will rate their perceived exertion on a 1-10 Borg CR₁₀ scale, with 1 representing very slight exertion, 5 being severe, and 10 representing maximal exertion. Perceived fatigue will be rated on a 0-10 ROF scale, with 0 representing not fatigued at all, 5 moderately fatigued, and 10 total fatigue & exhaustion. Two points difference on either scale will be considered a clinically important difference. Time the surgeon removes the sterile surgical gown and the cooling vest after completing the C3B will be recorded. Also, total amount of time the surgeon wore the sterile surgical gown / cooling vest in minutes will be calculated.

Ambient operating room temperatures will be monitored at ≤15-minute intervals with an electronic thermometer positioned eight feet from the base of the OR table, outside of the surgical field on the circulating nurses' workstation.

Data Analysis

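### The core and skin temperature averages have no start or stop time; read literally they include readings from before the vest is on, which pull the vest effect toward zero

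*Combined protocol and SAP*

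**What the plan says.** Under Measurements, Secondary Outcomes #1 and #2 are the mean core and mean skin temperature for a case, each "calculated as the time-weighted average over the taken measurements". Neither definition gives a start or a stop. The Data Analysis section (Specific Aim 2) models temperature during the case and does not define that period. The only stated exclusion, under Sample Size Justification, is poor data or lead disconnection.

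The sensor timeline is spread over several places:

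- The core sensor is applied to the "right axilla 15-20 minutes prior to the surgical hand scrub performed at the start of surgery".
- Under Protocol, the vest is "donned over hospital-issued scrubs after all temperature sensing devices have been applied and before surgical hand scrubbing".
- Also under Protocol: "Allocation for each case will be concealed with a web-based system that will be accessed only shortly before surgery".
- Under Secondary Outcome #2, sensors stay on "throughout surgery and approximately 10 minutes required for post-operative testing".
- Under Secondary Outcome #3: "The surgeons will sit with the iPad touch screen placed on a desk in front of them for approximately 10 minutes". The vest is still worn then and is removed after the C3B.
- Before each case, "the time the surgeon dons the cooling vest and the time the surgeon dons the sterile surgical gown will be recorded".

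Secondary hypothesis 1 is that mean body temperature, estimated from core and skin, "is reduced by wearing a cooling vest during prolonged and strenuous surgery".

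**The concern.** The hypothesis concerns temperature during surgery, but the only operating rule averages whatever the sensors recorded. Two kinds of non-surgical minutes can enter.

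The first is the time between sensor application and vest donning. No treatment has been given, so the expected vest-minus-control difference is zero. Averaging these minutes in shrinks the estimated difference in proportion to their share. Using the same window in both conditions does not prevent this; it makes the shrinkage systematic. The share also changes with case length.

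The second is the seated cognitive test after surgery. The Subject selection section excludes cases done seated on stools because sitting may affect temperature and energy expenditure. Including seated minutes in the outcome sits badly with that reasoning.

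An open window also leaves start and stop times to be chosen once the recordings are in hand, for outcomes tested at 0.017. Mean body temperature would inherit whatever window is used.

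**Working it through.** **Inputs from the documents.** n = 26; secondary significance criterion 0.05/3, stated as 0.017; detectable secondary effect size 0.76 at 90% power; scheduled case length 90-150 minutes; core sensor to hand scrub 15-20 minutes; about 10 minutes of post-operative testing.

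**Reproducing the plan.** Two-sided paired t-test, noncentral t, df = n − 1.

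- Primary: SD of the difference = √(2·9 − 2·0.5·9) = 3, effect 2/3, n = 26, alpha 0.05. Power is 0.904, which agrees with the stated 90%.
- Secondary: effect 0.76, n = 26, alpha 0.017. Power is 0.897 (0.895 at exactly 0.05/3), which agrees with the stated 90%.

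**How long is the pre-vest period?** The 15-20 minutes run from core sensor to hand scrub, and the vest goes on inside that interval. Pre-vest time P is therefore above 0 and below 15-20 minutes for the core sensor. Late access to the allocation suggests late donning but fixes no time. For the skin patches the documents say only that they precede the vest.

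**Share of the record.** f = P / (P + surgery + 10), with no gap assumed between hand scrub and the start of surgery.

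- Ceiling, long case: 15/(15 + 150 + 10) = 15/175 = 8.6%
- Ceiling, short case: 20/(20 + 90 + 10) = 20/120 = 16.7%
- P = 5 (assumption), long case: 5/165 = 3.0%
- P = 5, short case: 5/105 = 4.8%

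In the two ceiling records the seated test makes up 10/175 = 5.7% and 10/120 = 8.3%.

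**Retained effect and power.** Retained effect = 0.76 × (1 − f). Only pre-vest minutes are given zero effect. The SD of the difference is held fixed (assumption). Power is at n = 26, alpha 0.017.

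| Pre-vest min | Surgery min | Share | Effect | Power |
|---|---|---|---|---|
| 0 | any | 0 | 0.76 | 0.897 |
| 5 | 150 | 3.0% | 0.74 | 0.876 |
| 5 | 90 | 4.8% | 0.72 | 0.862 |
| 15 | 150 | 8.6% | 0.69 | 0.829 |
| 20 | 90 | 16.7% | 0.63 | 0.744 |

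**Sensitivity to the 10 minutes.** The sentence that keeps sensors on after surgery stands under the skin outcome. If the core sensor came off at the end of surgery, the ceiling shares would be 15/165 = 9.1% and 20/110 = 18.2%, with power 0.82 and 0.73.

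**The case against.** The strongest reply is that the text already points to a window. The outcome is a mean for a case, the model refers to temperature during the case, and the aim refers to surgery. The Methods section also promises a full statistical analysis plan before any data are evaluated, where a window would normally be set. This stands in part: inclusion of the pre-vest minutes is the literal reading, not an explicit instruction. But the narrower phrases are undefined, and the one rule that can be followed applies no limit.

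A reader might infer that 15-20 untreated minutes are averaged in for both outcomes. The documents do not support that. The figure is a ceiling for the core sensor, and the skin patches have no stated start time.

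A reader might also infer that the seated minutes dilute the vest effect. That is not supported either. The vest is still on, so these are treated minutes that are not surgery, and they could move the difference either way.

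The power figures are open to challenge, and the challenge is fair. The 0.76 is a detectable effect, not a predicted one, and could be read as applying to the outcome as literally defined. The calculation uses one paired difference per surgeon, as the plan does, although each surgeon contributes two cases per condition. If those are averaged and the vest effect does not vary between surgeons (assumption), the effective size is multiplied by √2, and the ceiling case (0.63) has about 97% power. The bias in the estimate remains whatever the power.

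Dependence on case length is not a separate objection to the plan, since any average over a 90-150 minute operation shares it.

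**Conclusion.** The concern holds in a limited form. The averaging window is not defined, and the rule as written admits some pre-vest readings that bias the vest-minus-control difference toward zero. On the stated record lengths the attenuation is at most 8.6-16.7% for core temperature, about 3-5% if pre-vest time is 5 minutes, and cannot be sized for skin temperature. The corresponding power is 88-86% at 5 minutes and 83-74% at the ceiling, against about 90% undiluted.

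These figures assume zero effect before the vest, an unchanged SD, the plan's one-difference-per-surgeon basis, actual durations equal to scheduled ones, and 10 post-operative minutes in the record. They illustrate scale and do not forecast power. The seated minutes fall outside the stated hypothesis, with unknown direction. The point affects secondary outcomes only. It should be fixed because the rule as written gives a worse estimate than one available from data largely already collected. Confidence is medium.

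**What to change.** In the SAP, define the averaging window for core and skin temperature identically in both conditions, from gown donning to end of surgery. Gown time is recorded in every case, whereas vest time exists only in vest cases. The vest is donned before the scrub and worn under the gown, so the window starts with the vest on.

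Name the end-of-surgery time. Gown removal cannot serve, because it follows the C3B. Options are surgery start plus the recorded procedure duration, provided the start time is captured, or one added stamp, for example when the surgeon leaves the field for the second oral temperature.

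Apply the same window to mean body temperature. Use the pre-vest readings as a per-case baseline covariate in the mixed model, with the baseline interval defined so that it can also be applied in control cases (for example, a fixed period after sensor application that ends before any vest is donned). Report the seated post-operative readings separately.

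The cost is a few sentences of SAP text, slightly fewer minutes per case, and possibly one extra time stamp.

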Participants' age, weight, height, and other continuous demographics and baseline characteristics will be summarized using descriptive statistics (n, mean, median, standard deviation, minimum and maximum), while race, surgical specialty, as well as other categorical variables will be summarized with frequency tabulations. The 4 sequence groups will be compared on baseline variables descriptively.

Specific Aim 1) Evaluate the difference between surgeons' self-rated thermal comfort with and without a cooling vest during prolonged and strenuous surgery. 0-10.

Perceived measure of thermal comfort for both conditions, with and without a cooling vest will be analyzed by descriptive statistics recommended for ordinal Likert scale items – i.e., frequencies and median [quartiles].

We will use a linear mixed effects model to test the treatment effect of the cooling vest on mean thermal comfort. We will adjust for treatment, sequence and period effects, and include subject as a random effect to account for the within-subject correlation. We will test for differential carryover effect by assessing the treatment-by-period interaction. If no interaction is detected the interaction term will be removed and the treatment effect assessed in a main effects model.

Specific Aim 2) Evaluate the difference between the surgeons' core, mean skin, and mean body temperatures with and without a cooling vest during a prolonged strenuous surgery.

For each temperature we will used a linear mixed effects model to test the treatment effect of the cooling vest on a subject's temperature during the case. We will adjust for treatment, sequence and period effects, and include subject as a random effect to account for the within-subject correlation. We will test for differential carryover effect by assessing the treatment-by-period interaction. If no interaction is detected the interaction term will be removed and the treatment effect assessed in a main effects model.

Specific Aim 3: Evaluate the difference between the surgeons' measure of cognitive performance with and without a cooling vest just after a prolonged strenuous surgery.

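### The two printed forms of the mean skin temperature formula are not equal: the second weights the leg 0.04 instead of 0.2, its weights sum to 0.84, and it reads about 5 °C low.

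*Combined protocol and SAP*

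**What the plan says.** The section Measurements, Secondary Outcome #2, sets the outcome out as follows: "The second secondary outcome will be the mean skin temperature for a case, calculated as the time-weighted average over the taken measurements". It then gives one bracketed formula containing two expressions joined by the word *or*.

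- The first is "0.3 t_{\text{chest}} + 0.3 t_{\text{arm}} + 0.2 t_{\text{thigh}} + 0.2 t_{\text{leg", in plain notation 0.3 × chest + 0.3 × arm + 0.2 × thigh + 0.2 × leg.
- The second is "0.3(t_{\text{chest}} + t_{\text{arm}}) + 0.2(t_{\text{thigh}} + 0.2 t_{\text{leg", in plain notation 0.3 × (chest + arm) + 0.2 × (thigh + 0.2 × leg).

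The result is used in two places. Data Analysis, Specific Aim 2, reads: "Evaluate the difference between the surgeons' core, mean skin, and mean body temperatures with and without a cooling vest", and fits a linear mixed model to each temperature. Secondary hypothesis 1 under Specific Aims reads: "Surgeons' mean-body temperature, estimated from core and mean-skin temperature, is reduced by wearing a cooling vest", so mean skin temperature is also an input to mean-body temperature.

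The formula is not repeated elsewhere, and nothing says which form will be programmed. The 1964 source cited for it does not appear in the reference list.

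**The concern.** The two expressions are offered as the same quantity, but the second multiplies the leg temperature by 0.2 inside a bracket that is already multiplied by 0.2. Someone could follow the printed plan exactly and still compute something that is not a mean skin temperature.

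This is the working definition of a numbered secondary outcome. The plan tests three secondary outcomes, described as two temperatures and cognitive function, each at 0.05/3 = 0.017. Core and mean skin temperature are the two temperatures defined as numbered outcomes, so mean skin temperature is very likely one of the three. Some doubt remains because Aim 2 lists three temperatures.

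At stake are the absolute skin temperatures to be reported, the mean-body temperature derived from them, and to a smaller degree the estimated vest effect.

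**Working it through.** **Inputs.** Both expressions come from Measurements, Secondary Outcome #2. The documents give no expected skin temperatures, so every temperature below is an assumption used to show size.

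**Step 1: weights.**

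| Site | First form | Second form |
|---|---|---|
| Chest | 0.30 | 0.30 |
| Arm | 0.30 | 0.30 |
| Thigh | 0.20 | 0.20 |
| Leg | 0.20 | 0.2 × 0.2 = 0.04 |
| Sum | 1.00 | 0.84 |

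The first form is a proper weighted mean; the second is not. The leg's coefficient falls to one fifth of its value in the first form. Its share of the total weight falls from 0.20 to 0.04/0.84 = 0.048.

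**Step 2: error in level.** First form minus second form = (0.20 − 0.04) × leg = 0.16 × leg.

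| Assumed leg temperature (°C) | Shortfall of second form (°C) |
|---|---|
| 28 | 4.48 |
| 30 | 4.80 |
| 32 | 5.12 |
| 34 | 5.44 |
| 35 | 5.60 |

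Two worked cases:

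- All sites at 33 °C. First form: 33.00. Second form: 0.3 × 66 + 0.2 × (33 + 6.6) = 19.80 + 7.92 = 27.72.
- Chest 33.5, arm 33, thigh 32.5, leg 31.5 °C. First form: 19.95 + 6.50 + 6.30 = 32.75. Second form: 19.95 + 0.2 × (32.5 + 6.3) = 19.95 + 7.76 = 27.71. The shortfall is 5.04 °C, and the result lies below the coldest site.

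For scale, the plan quotes an accuracy of ±0.5 °C for the core-temperature sensor.

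**Step 3: error in the vest contrast, with one form used throughout.** The error is 0.16 × the vest-minus-control difference at the leg, with the effect drawn towards zero when the vest cools the leg.

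| Assumed effect: chest, arm, thigh, leg (°C) | First form | Second form |
|---|---|---|
| −1, −1, −1, −1 | −1.00 | −0.84 |
| −1, −0.5, −0.2, −0.2 | −0.53 | −0.498 |
| −2, −1, 0, 0 | −0.90 | −0.90 |

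**Step 4: mean-body temperature.** The level error passes through multiplied by the weight given to skin temperature. The documents state no mean-body formula and no skin weight, so this part cannot be put in degrees.

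**Step 5: the corrected form.** 0.3 × (chest + arm) + 0.2 × (thigh + leg) has weights 0.3, 0.3, 0.2 and 0.2, which sum to 1.00. It returns 32.75 °C in the second worked case, as the first form does.

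**The case against.** The strongest reply accepts the algebra and disputes the consequence.

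- **The test is a within-surgeon contrast.** The level error cancels if one form is used throughout. The cooling packs sit on the shoulders, flanks and mid-back, well away from the calf. With assumed leg differences of 0.2 to 1.0 °C, the remaining error is 0.03 to 0.16 °C. This stands, and it is why the point is a correction and not a threat to the trial's conclusions.
- **The slip is easy to see.** The first form is complete, comes first and has weights that sum to 1, and a range check would probably flag values near 27 °C. That makes misuse less likely. It does not remove the ambiguity, because the text presents the second form as an equal alternative.
- **A full statistical analysis plan is still to be written, according to Methods.** That gives an opportunity to correct the formula, but nothing in the available documents does so.
- **PDF conversion may have moved a bracket.** If the source has 0.2 × (thigh) + 0.2 × leg, the second 0.2 is legitimate. This cannot be excluded from the text alone. A drafting slip in factoring the first form is more likely, and the original file will settle it.

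**Conclusion.** The concern holds. As printed, the two forms differ by exactly 0.16 × leg temperature, and the second has weights summing to 0.84. Those facts need no assumption. The figure of about 5 °C rests on an assumed leg temperature: 4.5 to 5.4 °C over 28 to 34 °C.

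The consequence depends on what is programmed. With the first form throughout, there is no error. With the second form throughout, absolute values are wrong and the vest effect is off by 0.16 × the effect at the leg. With the forms mixed across cases, differences of about 5 °C would enter the data as artefact. The primary outcome, the sample size, and the core-temperature and cognitive analyses do not use this formula.

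**What to change.** Check the source file, then either delete the second expression or correct it to 0.3 × (t_chest + t_arm) + 0.2 × (t_thigh + t_leg). State that the weights sum to 1.0 and that this is the form to be programmed, and carry the same line into the full statistical analysis plan. If any skin temperatures have already been derived, confirm which form was used and recompute from the site readings if it was the second.

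The cost is a one-line correction, with no change to the design, the measurements or the sample size.

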Environmental conditions (ambient OR temperatures, overhead lighting, electrical equipment), personal factors (personal protective equipment, metabolic heat, core and skin temperatures) and situational factors (type and length of a surgical procedure, perceived ergonomic workload) contribute to the presence of occupational heat stress experienced by surgeons performing surgical procedures. Surgeons' physiological and psychological responses to heat stress are measureable through a self-reported response to thermal comfort and perceived ergonomic workload, skin and core body temperature sensors, and a cognitive battery assessment. The physiological and psychological measure of surgeons' responses to heat stress can be influenced by wearing a cooling vest during the surgical procedure (Figure 1).

[figure not shown]

Figure 1. Conceptual Framework.

Methods

The trial will be conducted with Cleveland Clinic IRB approval and consent from participating surgeons. The trial will be registered at ClinicalTrials.gov. A full statistical analysis plan will be developed before any data are evaluated. Reporting will be consistent with the CONSORT guidelines.

Subject selection

Inclusion criteria are: 1) surgeons who perform elective major orthopedic surgery such as total hip and knee arthroplasties scheduled for 90 to 150 minutes at the Cleveland Clinic Main Campus; 2) Orthopedic surgeons ages of 25-65 years old, as body temperatures may be lower and less stable

in the elderly (Waalen & Buxbaum, 2011), who operate frequently enough to participate in four cross-over cases; 3) Surgical procedures in which surgical helmet systems or airborne barrier protection devices are worn are included as long as the surgeon wears the system for all four cases being measured.

Exclusion criteria are: 1) Surgical cases that require surgeons to sit on stools during the procedure, which may impact temperature and energy expenditure; 2) Surgeons who report having a recent illness within 24 hours prior to the surgery, symptoms producing a febrile condition; 3) Surgeons who worked the previous evening; and 4) Surgeons who wear lead X-ray gowns.

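### Thermal comfort and fatigue are rated only after surgery; a rating before the vest goes on, used as a covariate, would sharpen the vest comparison at little cost (a matter of precision, not bias)

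*Combined protocol and SAP*

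**What the plan says.** Under Measurements, the primary outcome is a single rating per case, given immediately after surgery with the gown still on: "surgeons will rate their thermal comfort on a 0-10 Likert scale, with 0 representing extreme cold, 5 being thermal comfort". Exertion and fatigue (Secondary Outcome #4) are collected at the same moment: "surgeons will rate their perceived exertion on a 1-10 Borg CR₁₀ scale", and "Perceived fatigue will be rated on a 0-10 ROF scale, with 0 representing not fatigued at all, 5 moderately fatigued". No pre-case rating of any of the three is planned.

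Other measurements do have a pre-case value. "The sensor will be applied to the surgeon's right axilla 15-20 minutes prior to the surgical hand scrub performed at the start of surgery". "After the temperature sensors are applied, the surgeon's oral temperature will be measured". For the C3B at cases after the first assessment, "the test will be administered prior to the surgical hand scrub and after the end of surgery". The Protocol section puts the vest on after the sensors and before the scrub, and has the allocation for each case opened only shortly before surgery.

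Under Data Analysis, Specific Aims 1 and 4 use a linear mixed model with treatment, sequence and period, and surgeon as a random effect. There is no case-level baseline term.

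Starting state is partly limited. Subject selection excludes recent febrile illness and "Surgeons who worked the previous evening". The Protocol section aims for the same room temperature across a surgeon's four cases. Hours slept are recorded, although Specific Aim 4 lists them as part of the workload measure rather than as a covariate. No rule fixes where a study case falls in the operating day.

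**The concern.** A rating given at the end of a case reflects both the case and the state in which the surgeon began it: sleep, earlier operations that day, time already spent in a gown. The random surgeon effect removes stable differences between surgeons. It does not remove differences between one surgeon's own four cases, and those are the comparisons on which the trial rests.

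At stake is the width of the confidence interval for the vest effect on thermal comfort and fatigue, and the ability to describe how much of a post-case score was already present at the start. A rating not taken at the time cannot be obtained later.

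**Working it through.** **Inputs from the documents.** SD 3 per condition, within-subject correlation 0.5, target difference 2, significance level 0.05, power 90%, 26 surgeons (Sample Size Justification); two cases per condition per surgeon (Protocol). **Assumption:** r, the within-surgeon correlation between pre-case and post-case rating. The documents give none; their 0.5 is between conditions. I use 0.3, 0.5 and 0.7.

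**1. The plan's own figure.** SD of the within-subject difference = √(2×9 − 2×0.5×9) = 3. A two-sided paired t-test at 0.05 for a difference of 2 needs 26 surgeons, with power 0.904 at 26. The stated sample size is reproduced, and it assumes no baseline.

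**2. Standard error with post-case ratings only.** Reading the SD and correlation per case, the residual variance is 9 × (1 − 0.5) = 4.5. With 26 × 2 = 52 cases per condition, SE = √(4.5 × 2/52) = 0.416.

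**3. Standard error with the pre-case rating as covariate.** The residual variance is multiplied by (1 − r²), so the SE is multiplied by √(1 − r²).

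| r (assumed) | Share of residual variance removed | SE | Reduction in SE |
|---|---|---|---|
| 0 | 0% | 0.416 | none |
| 0.3 | 9% | 0.397 | 5% |
| 0.5 | 25% | 0.360 | 13% |
| 0.7 | 49% | 0.297 | 29% |

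At r = 0 the cost is one of 104 − 26 − 3 − 1 = 74 within-surgeon degrees of freedom. No SD is given for fatigue, so only the proportional reduction carries over to that outcome.

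**4. Does primary power need it?** On the same per-case reading, the SD of a surgeon's difference between two-case means is √(4.5 × (1/2 + 1/2)) = 2.12. Then 14 surgeons give 90% power and 26 give 0.996. On the plan's own paired basis (SD 3), power at 26 would rise from 0.904 to 0.928, 0.965 or 0.995 at the three values of r.

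**5. Covariate or change score?** With equal variances, a change score multiplies the variance by 2(1 − r), which exceeds 1 whenever r < 0.5. On the plan's paired basis at r = 0.3, power at 26 falls to 0.788 and 36 surgeons would be needed.

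**6. Is the vest contrast biased without it?** Across ABBA, BAAB, AABB and BBAA, the successions AA, AB, BA and BB each occur three times, so first-order carried-over heat is balanced between conditions. The planned crossover was simulated with 26 surgeons, a true difference of 2 and 2,000 runs per setting. Bias of the post-only estimate stayed within 0.02 points, even with a 2-point shift in the next case's starting state after a no-vest case. With no true difference and a 1-point shift (4,000 runs per setting), its type I error was 0.042 to 0.050. The simulated SD of the estimate was about 0.41 for post-only ratings and 0.39–0.41, 0.36 and 0.29–0.30 with the covariate, in line with step 3.

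**The case against.** The strongest reply is that this is optional. Every aim is a within-surgeon contrast under randomised order, so starting state is balanced in expectation, and any chance imbalance is ordinary sampling error already counted in the standard error. That stands.

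It also stands that the documents are not silent on starting state. Besides the exclusions and the room temperature target, they record hours slept, pre-case oral temperature and the time of gowning. These allow an indirect check of imbalance in sleep, warmth and time of day.

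The remedy has limits too. A resting exertion score would mean little on a scale whose lowest anchor, 1, is very slight exertion. A rating before allocation is not always blind to the coming condition: in the four sequences the first two cases determine the last two (AB is followed by BA, AA by BB, and so on), and Protection of Human Subjects says participants are told the whole protocol. A surgeon who knows the sequences can work out cases 3 and 4. The earlier answer may also anchor the later one.

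What remains is that the indirect measures are not ratings of comfort or fatigue, none of them enters the models, and a direct rating is nearly free at a contact that already takes place.

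**Conclusion.** A minor, low-cost gain in precision. With the plan's SD and correlation read per case, the standard error of the vest effect on thermal comfort would fall from 0.42 to about 0.40, 0.36 or 0.30 at an assumed r of 0.3, 0.5 or 0.7, with essentially no gain if r is near zero.

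Stronger readings are tempting, but the documents do not support them:

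- A reader might infer that carried-in heat or fatigue is credited to the vest or to its absence. Randomised, strongly balanced sequences make it noise. Because 26 is not divisible by 4, and cases may be missed, balance may be slightly imperfect, but nothing indicates a material bias.
- A reader might infer that a pre-case rating would eliminate the problem. It removes only a share r² of the residual variance.
- A reader might infer that the primary test is underpowered without it. The plan's figure reproduces, and power is about 0.996 on the per-case reading.
- A reader might infer that starting state is uncontrolled and cannot be examined. It is partly controlled, and indirect data are collected.

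**What to change.** At the sensor and oral-temperature contact, have the surgeon give the same 0-10 thermal rating and the ROF rating, but not exertion. State explicitly that this comes before the case's allocation is opened and before the vest is donned. "Before scrub" alone is not enough, because the vest also goes on before the scrub, and adjusting for a rating taken after that could remove part of the vest effect. The sensor contact is a safer anchor than the C3B, whose pre-scrub administration is described only for subsequent cases.

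In the analysis plan, enter the pre-case rating as a covariate in the model for the same outcome, split into the surgeon's mean over their cases and the deviation of each case from that mean. Do not analyse change scores. Keep the unadjusted model as a sensitivity analysis, because of possible anchoring and because the condition at cases 3 and 4 can be inferred. Record the case's position in the surgeon's operating day.

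The cost is two ratings and one extra field, under a minute per case with existing staff, plus a short amendment. The reassessment after 13 surgeons could then also estimate r.
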